11.1 Hypothesis

The two-sided null hypothesis to be tested is that nasal cavity photodisinfection by aPDT (intervention) as an add-on treatment to 0.2 % chlorhexidine gluconate has no effect on local microbial colonization in a perioperative setting compared to 0.2 % chlorhexidine gluconate and non-light activated methylene blue (control). The corresponding alternative hypothesis is that the two treatments differ. The research hypothesis is, that the intervention will reduce local microbial colonization compared to control (superiority of the intervention).

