11.2 Determination of sample size

The sample size was calculated to show the superiority of the intervention compared to the control regarding the primary outcome with a power of 90 % at a significance level of 5 %. We calculated the sample size for a Wilcoxon-Mann-Whitney test, but did this via the sample size for a two-sample t-test and by increasing the sample size using the Asymptotic Relative Efficiency (ARE) of the Wilcoxon-Mann-Whitney test (compared to the t-test), which is never less than 0.864 (17,18). The power was estimated for a range of sample sizes $n_{i=1,\dots,61} = 50,\dots,350$ with the R package sse (19). Moreover, to assess how the calculation is affected by the mean difference, θ , we varied θ from 1.5 to 4.5. For each combination of n_i and θ , we calculated the power for a two-sample t-test.

Figure 1 shows that for showing a mean difference in the primary outcome of 3 with a standard deviation of 6, a total of 170 evaluable patients would be required for a two-sample t-test. For a Wilcoxon-Mann-Whitney test we increased the sample size, dividing 170 by 0.864, which resulted in 198 patients (rounded up to an even number). Assuming a drop-out rate of 5 %, 208 patients need to be enrolled.

[figure not shown]

Figure 1: Dependence of the sample size on the mean difference between treatments, θ , assuming a standard deviation of 6. An example is shown for $\theta=3$ and a power of 90 %. The curves are smoothed and shown for illustration only.

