11.4.3 Secondary analyses

Analyses of secondary outcomes: The secondary outcome, bacterial colonization 14 days after aPDT (measured otherwise the same way as the primary outcome) and bacterial colonization 2 days after for the ORIF midface group will be analyzed in a similar way as the primary outcome (see Section 11.4.2). The proportional odds logistic regression model will additionally adjust for concomitant treatment with nasal rinse therapy, antibiotic therapy, steroid therapy, and nasal decongestant therapy, which are prescribed depending on the surgical intervention, and may also influence bacterial colonization after 14 days. To compare bacterial colonization 5 minutes after aPDT 2 days (only ORIF midface) and 14 days after aPDT (short- and long-term), we analyze these measurements as repeated measurements together in one model. We fit a mixed-effects proportional odds logistic regression model on bacterial colonization, with treatment (intervention vs. control) and time (14 days vs. 5 min and 2 days (only ORIF midface)) as explanatory variables. In an additional model, we will add the interaction between treatment and time, in order to test for a difference in the change over time between the treatment groups.

The colonization with individual types of bacteria (9 types) at baseline, and 5 minutes and 2 days (only ORIF midface) and 14 days after aPDT will be descriptively analyzed and summary statistics (frequency and percentage of each category) will be reported by treatment group.

Subgroup analyses: For the primary outcome, subgroup analyses will be performed for the following subgroups: bacterial colonization at baseline ($>$ median vs \geq median), type of surgery and sex. For each subgroup variable, a proportional odds logistic regression model will be fitted to the primary outcome, with treatment, the subgroup variable, and the interaction between the subgroup variable and treatment as explanatory variables. A statistically significant interaction between one of the subgroup variables and treatment would indicate a different treatment effect in the corresponding subgroups. We will also estimate group-specific treatment effects (with 95 % CI), fitting a separate model for the corresponding subgroups, which will be reported together with the interaction p-value.

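### The treatment interaction with baseline colonization is tested on a median split of a 0–27 score, and the three subgroup interactions carry no exploratory label; both are cheap to improve

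*Combined protocol and SAP*

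**What the plan says.** Under Subgroup analyses, Section 11.4.3 states that "subgroup analyses will be performed for the following subgroups: bacterial colonization at baseline", divided at the median, followed by type of surgery and sex. Each variable gets its own proportional odds model with treatment, the subgroup variable and their interaction. The reading rule is: "A statistically significant interaction between one of the subgroup variables and treatment would indicate a different treatment effect in the corresponding subgroups". Effects within subgroups come from "fitting a separate model for the corresponding subgroups, which will be reported together with the interaction p-value".

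Three further facts matter.

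- Section 9.2.2 says the baseline swab is scored on the same 0–27 scale as the outcome, so the ungrouped value is in the data.
- The only significance level in the documents is the one used for the sample size, "regarding the primary outcome with a power of 90 % at a significance level of 5" per cent (Section 11.2). No level, multiplicity rule or exploratory label is given for the interaction tests.
- The opening of Section 11 defers detailed methodology to a statistical analysis plan to be finalized before database closure.

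As printed, the two halves are defined with a greater-than sign and a greater-or-equal sign. These groups overlap and leave out values below the median. This may be an artefact of reading the PDF.

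**The concern.** Cutting a 28-value score into two groups treats a patient just above the median like the most heavily colonized patient. If the treatment effect changes steadily with baseline colonization, the split test is less able to show it, although the finer data are already in hand.

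The reading rule treats a significant interaction for any one of the variables as showing a different effect, and nothing marks these analyses as exploratory. Section 13 promises publication of an analysis of gender effects, and Section 4.3 aims at a disinfection protocol for the hospital. A chance interaction could therefore be given more weight than it can bear.

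**Working it through.** **The plan's own figure.** The plan gives no power or error rate for the interactions, so only its sample size can be reproduced. It is two-sided (Section 11.1), with 90% power, 5% level, difference 3 and SD 6. Per arm, 2 × (1.960 + 1.282)² × (6/3)² = 84.1, rounded up to 85, so 170 in total. Then 170/0.864 = 196.8, rounded up to an even 198, and 198 × 1.05 = 207.9, so 208. These match the documents. They concern the main comparison only.

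**Information kept by a median split.** For a linear effect, the share kept is the squared correlation between the score and its split indicator.

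- Normal score: covariance 0.3989 per SD, indicator variance 0.25. Share = 0.3989²/0.25 = 2/π = 0.637, so the loss is 36%. Of 198 evaluable patients, the split then carries the information of 0.637 × 198 ≈ 126.
- Uniform score: covariance 0.125, variances 1/12 and 1/4. Share = 0.125²/(1/48) = 0.75, so the loss is 25%.
- Normal scores rounded to integers on 0–27 (several means and SDs): loss 32–36%.
- Right-skewed integer scores (rounded gamma, shapes 1 to 3): loss 40–73%, depending on the skewness and on which half takes the ties at the median.

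**Power for the baseline interaction.** The documents give no interaction size, so these settings are assumptions. All use a linear interaction and a 5% test.

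| Simulation | Setting | Ungrouped | Split |
|---|---|---|---|
| Proportional odds, n = 208, 12-level outcome, 400 trials each | no interaction | 4.5% | 4.3% |
| | log odds ratio −0.5 per baseline SD | 52.5% | 32.5% |
| | log odds ratio −0.8 per baseline SD | 86.8% | 68.8% |
| Linear model, n = 198, 2,000 trials each | slope 0.3, baseline–outcome correlation 0.3 | 59% | 39% |
| | slope 0.3, correlation 0.6 | 73% | 43% |
| | slope 0.4, correlation 0.3 | 83% | 62% |
| | slope 0.4, correlation 0.6 | 93% | 66% |

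The proportional odds interactions are large. Between one SD below and one SD above the mean, the treatment odds ratio changes by a factor of exp(2 × 0.5) = 2.7 or exp(2 × 0.8) = 5.0.

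**When the split wins.** With a threshold interaction in a linear model at n = 198, power was 36% for the ungrouped score and 46% for the split. This is expected: for a normal score and a true step at the median, the squared correlation works the other way and the linear term keeps only 64%.

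**False interactions.** Assuming 5% per test and independence, 1 − 0.95³ = 0.1426. A simulation under no interaction (6,000 trials, surgery type as one test on 2 degrees of freedom) gave 14.5% with independent subgroup variables and 13.8% with mildly correlated ones. This is the chance of at least one false finding among three; each single test keeps its own 5%.

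**The case against.** The strongest reply is that this is a restrained plan: three prespecified variables, judged by interaction tests and not by comparing p-values within subgroups. The reading rule ends by referring to the corresponding subgroups, so each result can be taken as speaking only for its own variable. Detail is deferred to a later analysis plan. Much of this stands and limits the point. The deferral does not remove it, because Section 11.4.3 already fixes the split and the reading rule.

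A reader might infer more than the documents support:

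- *That the subgroup plan as a whole loses a third of its information.* Only the baseline interaction is affected, and the figure depends on an unknown distribution and shape.
- *That baseline colonization is the one plausible modifier, because a lightly colonized patient cannot fall far.* That argument concerns absolute change in score; on the planned odds-ratio scale a floor does not by itself create an interaction. Section 6.2.1 also describes surgery types as differing in age, comorbidity and concomitant treatment.
- *That a formal multiplicity correction is needed.* With Holm, the first step is at 0.05/3 = 0.0167 (critical value 2.394 in place of 1.960). By normal approximation, the ungrouped power of 53% falls to about 36% and 87% to about 75%, against 33% and 69% for the split at 5%. The correction would give back most of the gain, and an honest label answers the concern.
- *That subgroup estimates from separate models are an error.* They need not agree exactly with the joint-model p-value, but they assume less, because each subgroup has its own cutpoints. No size of disagreement has been shown; the choice is a preference.

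**Conclusion.** The point holds as a minor improvement.

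- For the baseline interaction alone, the median split loses about 36% of the information if the score is roughly normal and the interaction linear. The loss was 25% to 73% across the distributions tried, and the ranking can reverse under a threshold effect.
- The chance of at least one false interaction is about 14%. This assumes 5% per test, which the documents do not state for these tests, and near-independence.
- The absence of a multiplicity rule and an exploratory label is read from the documents' silence.

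None of this touches the primary test, its significance level or the sample size. A reader who took it as a threat to the main conclusion would be going beyond the documents.

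**What to change.** In Section 11.4.3 or the analysis plan that follows it:

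1. Test the baseline-by-treatment interaction with the ungrouped 0–27 score.
2. From that model, report the treatment odds ratio with 95% confidence interval at the 25th, 50th and 75th baseline percentiles.
3. Keep two halves for display and as a check on the shape, defined as at or below the median against above it. With ties they will be unequal: in the rounded normal scores tried, 43–47% of values lay above the median.
4. Replace the reading rule with wording such as: *The three interaction results are hypothesis-generating; a small p-value will be reported as a signal for further study and not as evidence of a different treatment effect.* No Holm adjustment is needed.

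The cost is a few sentences and slightly different code, with no new data, visits or patients. The statistical price is that the test assumes a linear interaction on the log-odds scale and can be less powerful if the truth is a threshold. The change should be made before database closure. If it is judged substantial, Sections 2.9 and 11.4.6 would call for an amendment.

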11.4.4 Interim analyses

None.

11.4.5 Safety analysis

Adverse effects (inquired by standardized survey on first day post intervention and on day 14 (+/- 1d) during regular postoperative follow up will be analyzed descriptively, with summary statistics reported by treatment group.

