MedDO	Medical Devices Ordinance
MD	Medical Device
MDR	Medical Device Regulation (EU) 2017/745 of 5 April 2017
MKG	Mund-, Kiefer- und Gesichtschirurgie
ORIF	Open Reduction and Internal Fixation
PCR	Polymerase Chain Reaction
PI	Principal Investigator
SADE	Serious Adverse Device Effect
SAE	Serious Adverse Event
SARS-CoV-2	severe acute respiratory syndrome coronavirus type 2
SNCTP	Swiss National Clinical Trials Portal
SOP	Standard Operating Procedure
USADE	Unanticipated Serious Adverse Device Effect
USZ	University Hospital Zurich

INVESTIGATION SCHEDULE

Table 1: Contact with study participants and procedures accomplished at each study visit

	Visit Number	0	1	2	3	4	5	x
	Visit Name	Patient enrolment	nasal decolonization	nasal decolonization	postoperative survey	nasal swab trauma subgroup	survey regular follow up 14d (+/-1)	unscheduled visits d 1-14
	Time*	min -1day	-3 minutes	+5 minutes	1 day	2 days	14 (+/-1) days	any
	Repeated event?	no	no	no	no	no	no	no
Repeated	Form name							
no	Informed consent; Inclusion / exclusion criteria	x						
no	Visit	x	x		x	x	x	x
no	Randomization		x					
no	Demographics	x						
no	Medical history	x						
yes	Survey concomitant treatment	x			x		x	x
no	Nasal swab* and microbiom data (*contains info on Intervention only in event +5 min)		x	x		x	x	
no	Survey expected side effects **				x		x	x
yes	SAE and device deficiency (templates from CTC, not part of PL)		x		x	x	x	x
no	Device deficiencies		x					
no	Study End						x	

*Study or control-Intervention = Timepoint 0

** For outpatients "Survey expected side effects" is carried out by telephone

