5.3 Safety outcomes

Standardized survey for adverse effects noted after treatment and on day 1 and day 14 (+/-1) during regular follow-up consultation after surgery. For outpatient procedures, side effects are surveyed after treatment on the first day as a telephone conversation.

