9.2.2 Assessment of secondary outcomes

Microbiological testing

The same score ranging from 0-27 is also used to express the colonization 3 minutes before intervention (baseline swab) and 14 (+/-1) days after study or control intervention (follow-up swab). Statistical analysis of baseline, post intervention and follow-up colonization scores allow for understanding the general effects of aPDT on nasal microbiota over a time period of 14 days. Analyzing the difference in microbial colonization scores of experimental and control groups between baseline, 5 minutes post intervention and 14 days after allows quantification of potential influence of concomitant treatment or disinfection effects of unactuated photosensitizer solution (methylene blue, chlorhexidine gluconate).

Only for the subgroup (open reduction and internal fixation of a midface fracture), an additional nasal swab test after 2 days is carried out. This additional testing allows for better understanding of the short-term effects with clinical importance in the initial wound healing. The reason for testing only the subgroup is mainly in the comparable postoperative management in terms of concomitant treatment (single shot antibiotic prophylaxis, CHX mouth rinse, decongestant nasal drops), duration of surgery and hospital stay.

To analyze for shifts within the microbiological colonization without change in total number of CFU, a descriptive subgroup analysis of the nine microbial groups is performed.

Obtaining personal data

Data on concomitant treatments will be taken from clinical information system KISIM.

Survey

The standardized survey for expected aPDT side effects will be conducted during clinical visit on the first postoperative day and regular 14 day (+/- 1d) postoperative follow-up.

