9.2.3 Assessment of safety outcomes

9.2.3.1 Adverse events

Adverse events will be documented in the eCRF. The type of adverse event, its severity or intensity, time of onset and occurrence, duration, resolution, and association with the medical device will be recorded. It will be noted whether an adverse event is to be classified as expected/unexpected and serious. All immediate local treatment effects and all delayed local effects will be recorded to assess safety. At the second visit, participants will be asked about any adverse effects that occurred in the meantime (14; +/- 1 days).

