10.3 Documentation and reporting in medical device category A clinical investigations

Device deficiencies (DD) and all adverse events (AE) including all serious adverse events (SAE), will be recorded, fully investigated, and documented in the source document and corresponding case report form (eCRF) throughout the investigation period (from patient consent to the last CIP-specific procedure).

- Documentation of AEs (including SAEs) by the PI includes diagnosis or symptoms, date of onset and end of the event, treatment, resolution, severity assessment, and causal relationship to MD and/or investigation procedure (Art. 32 ClinO-MD, ISO14155).
- Documentation of DDs by the PI includes a description of the dysfunction, date of onset, investigational device information, any action taken regarding the investigational device, and whether the DD led to an AE. The principal investigator shall review all DDs and determine and document in writing whether they could have led to an SAE (DD with SADE potential) (Art 32. ClinO-MD, ISO14155).
- The information on AEs is systematically collected by clinical safety assessment at the regular visits
- no safety follow-up is required based on the benefit-risk profile and lack of known long-term adverse effects with this medical device

Safety and protective measures

If immediate safety and protective measures must be taken during the conduct of this clinical trial, the investigator must notify the CEC of these measures and the circumstances necessitating them, within 2 days.

Annual Safety Report

(As indicated under 10.3.2)

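### The only by-arm safety summary planned is of survey answers on day 1 and day 14; other recorded AEs, SAEs and device deficiencies have none, and Table 1 schedules no form for non-serious AEs

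*Combined protocol and SAP*

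**What the plan says.** The safety outcome in section 5.3 is a survey: "Standardized survey for adverse effects noted after treatment and on day 1 and day 14 (+/-1) during regular follow-up consultation after surgery". The safety analysis in section 11.4.5 follows it. Its subject is "Adverse effects (inquired by standardized survey on first day post intervention and on day 14 (+/- 1d"), to be summarised descriptively for each treatment group. No other safety analysis is described.

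The survey's scope is described in two ways. Section 9.2.2 says "The standardized survey for expected aPDT side effects will be conducted during clinical visit on the first postoperative day" and at the 14-day follow-up, and the Table 1 row is named "Survey expected side effects". Section 9.2.3.1, by contrast, says that participants are asked at follow-up about any adverse effect since the intervention.

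The recording duties are wider than the survey. Section 10.3 requires that device deficiencies and "all adverse events (AE) including all serious adverse events (SAE), will be recorded, fully investigated, and documented", from consent to the last study procedure. Section 9.2.3.1 adds: "All immediate local treatment effects and all delayed local effects will be recorded to assess safety". Section 9.3.2 (in theatre) calls for the matching eCRF forms when an AE, SAE or device deficiency occurs. Sections 9.3.3 (day 1) and 9.3.5 (day 14) list AE/SAE recording separately from the survey. Section 9.3.4 (day 2) mentions only a swab.

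Table 1 has a row "SAE and device deficiency (templates from CTC, not part of PL"), a second row for device deficiencies, and the survey row. No row is named for non-serious AEs.

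**The concern.** The protocol asks the site to collect a full safety record and then plans to compare the arms on part of it. Followed as written, the by-arm safety result would contain no SAE, no event seen in theatre, no device deficiency and no report from an unscheduled visit, unless the patient also mentioned the event in the day-1 or day-14 survey.

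This matters more than usual here because section 6.1 names misattribution of immediate adverse effects, when the intervention is combined with surgery under general anaesthesia, as the design's main limitation. The randomised control arm is the natural protection: both arms have the same range of operations, so an excess in one arm is informative whatever cause was assigned to each event. For events outside the survey, no such comparison is planned. Patients are anaesthetised during the intervention, so events at that moment reach the record through the AE, SAE and deficiency forms and not through an interview.

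**Working it through.** The safety analysis states no figure to reproduce, so the check is to set the recording rules, the schedule and the analysis side by side.

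| Safety record | Required by | Scheduled in Table 1 | Summarised by arm in 11.4.5 |
|---|---|---|---|
| Survey answers, day 1 and day 14 | 5.3, 9.2.2, 9.3.3, 9.3.5 | Yes | Yes |
| Survey answers, unscheduled visits | Table 1 | Yes | No; only day 1 and day 14 are named |
| Non-serious AEs outside the survey | 9.2.3.1, 9.3.2, 9.3.3, 9.3.5, 10.3 | No row | No |
| SAEs | 9.2.3.1, 9.3.2, 9.3.3, 9.3.5, 10.3 | Theatre, day 1, day 2, day 14, unscheduled | No |
| Device deficiencies | 9.3.2, 10.3 | Joint row with SAEs, plus own row in theatre | No |

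One of the five kinds of record is in the planned by-arm summary.

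Other places where a summary might be found:
- Section 10.2 sorts every event into AE, ADE, SAE, SADE or USADE, but no tabulation of the result is planned.
- Section 10.3.2 puts SADEs and device deficiencies in the Annual Safety Report as a list with severity and causal relation. No split by arm is stated.
- The opening of section 11 defers detailed methods to a statistical analysis plan to be final before database closure. It commits to no AE table.

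Table 2 in section 3.7 is the only numerical material on the split between expected and unexpected effects. Its totals add up:
- During treatment: 246 + 67 = 313.
- Within 24 hours: 2,087 + 615 = 2,702.
- Total: 2,333 + 682 = 3,015.

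The share classed there as unexpected is 682 / 3,015 = 22.6%. The 71 unspecified others lie outside the printed totals; counting them as unexpected gives (682 + 71) / (3,015 + 71) = 753 / 3,086 = 24.4%. These are shares of reports in an industrial setting under that table's own classification. They would carry over only if this trial's survey used exactly that table's expected list, which the documents do not say.

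**The case against.** Several points on the other side stand, and they limit what can be claimed.

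- A reader might infer that these events will never be compared by arm. That is too strong. The later statistical analysis plan may add AE, SAE and deficiency tables; what can be said is that this document plans none.
- A reader might infer that non-serious AEs go uncollected. That is not shown. Sections 9.2.3.1, 9.3.2 and 10.3 require them to be documented, the survey catches some, and Table 1 itself notes that some templates lie outside it. The fault is that the schedule does not match the text.
- A reader might infer that the survey can detect only pre-listed symptoms. Section 9.2.3.1 points to an open enquiry at follow-up, and sections 5.3 and 11.4.5 do not restrict the effects to expected ones. The documents disagree on scope and do not settle it.
- A reader might use Table 2 to say that about one side effect in four or five, including all nosebleeds and headaches, would be missed. The survey items are not in the documents, and section 3.7's own prose names headache and nosebleed among reported effects, so this does not follow.
- The safety objective in section 4.4 concerns effects related to the nasal decolonisation, not every event after maxillofacial surgery. That narrows the gap between objective and analysis. It does not close it, because an SAE or in-theatre event may be related, and comparing arms is the way to find out.
- SAEs and device deficiencies reach the sponsor-investigator within 24 hours, and possibly related SAEs go to the ethics committee. This makes an unnoticed serious signal less likely, but it is case reporting and not a comparison of arms.

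**Conclusion.** The point holds as an omission in sections 5.3 and 11.4.5 and a mismatch between Table 1 and the visit and safety text. As written, the by-arm safety result leaves out SAEs, device deficiencies, unscheduled-visit reports, and in-theatre or other AEs not repeated in the day-1 or day-14 survey. This rests on the document's wording alone and does not depend on what the survey asks.

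Its size is one kind of safety record covered out of five. No number of missed events can be given, and the 22.6% and 24.4% from Table 2 should not be used as one. The point is worth correcting because the data are already required and the change is small. It is not evidence that safety data will be lost or that a signal will be hidden.

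**What to change.** 1. In 5.3 and 11.4.5, state that all recorded AEs, ADEs, SAEs, SADEs and device deficiencies from the start of the intervention to the day-14 visit, including the theatre visit, day 2 and unscheduled visits, are summarised descriptively by arm. Give patients with at least one event, number of events, seriousness and relatedness. Name the survey as one source.
2. Add a repeating AE row to Table 1 so that the schedule matches the visit text and section 10.3.
3. Reconcile Table 1 and section 9.2.2 with section 9.2.3.1 on whether the survey includes an open question about any adverse effect.

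The table definitions can go in the statistical analysis plan, but the AE form belongs in the schedule, because a later analysis plan cannot recover events that were never entered. The cost is protocol wording, one repeating eCRF form, and slightly more data entry and tabulation. No visits, staff or patients are added.
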